Data collection

Participants attended the lab at 8 am with light clothing and were asked a series of questions to measure fasting, nutrition, physical activity and sleep regimen adherence. They were also required to hand in the completed questionnaire which consisted of dietary and physical activity information which were distributed to them before data collection. Then, height, weight, waist circumference, % body fat and blood pressure measurement were taken followed by a perceived satiety measurement and fasting capillary blood sample (baseline) withdrawal using the finger pricking method.

After that, the participants were randomized to consume one of the two types of test products namely A: control (glucose) and B: Formulation 3 (60% sweetener) dissolved in 180 mL plain water together with the standardized breakfast in treatment sequences (AB, BA). Each respondent consumed the meals in a separate place and avoided using electronic gadgets while eating to reduce distractions. They were instructed to consume the meals at a comfortable pace within 15 min. Participants were asked to remain rested in the same place during the testing period and allowed to read, use their phone or laptop and use the toilet after meals consumption. They have also refrained from excessive physical activity until the end of test visit.

At the first bite, a timer was started and postprandial blood samples as well as perceived satiety measurement were then taken at 30, 60, 90 and 120 min thereafter. Blood collection techniques adhered exactly as they were written in the standard operating procedure (SOP). After the 120 min assessments, participants were allowed to leave the testing site and instructed to record the food consumed for the rest of the day. The food record was aimed to explore the changes in food intake following each test food relative to usual food intake (baseline data) (Burton-Freeman et al., 2017). Also, they were given a new food log form and physical activity diary to fill in one day before the next study visit. Figure 3.4 displayed the study flow chart.

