Acute Effect of Melon Manis Terengganu Peel Powder on Glycemic Response, Satiety, and Food Intake in Adults at Risk for Type 2 Diabetes

NCT05298111

25 March 2022

Statistical Analysis Plan (SAP)

Data Checking and Normality Test

Data entry errors and respondent's errors may occur during data entry and answering the questionnaire. Data were checked after they were entered into the SPSS. Data checking was crucial to ensure the accuracy of all the entered data, identify any missing data and any outliers during the data entry. Mistyping responses or entering data was an example of data entry errors in contrast to respondent's errors that happened during answering the questionnaire, for example the participants did not complete the questions or provide an unreadable or illogical response.

Before descriptive statistical analysis was performed, the frequency distribution (histogram) and boxplot were used for checking normality visually. Normally distributed population generated a bell-shaped curve appearance of the histogram with symmetrical about the mean indicates data. Besides, the Shapiro-Wilk test was done for the assessment of normality tests and the data considered to be normal if $p > 0.05$. Hence, according to the findings, the data checkinwas g revealed that all the variables have completed 30 valid frequencies for socio-demographic, anthropometry, biochemical, blood pressure, dietary intake, perceived satiety and physical activity information. Those outputs implied that no missing data value was reported.

Statistical Analysis

The data were analysed by using IBM SPSS system version 21.0 and Nutritionist ProTM software (Version 7.0.0, Axxya Systems).

Descriptive Statistic

A descriptive statistic was used to present all outcomes on socio-demographic information, anthropometric measurement, blood glucose levels, blood pressure measurement, dietary intake, perceived satiety and physical activity. Continuous data were described as mean \pm standard deviation if normally distributed or median (interquartile range) if not normally distributed meanwhile for categorical variables, the data were reported as the number of frequency and percentage. The 2 hr area under the curve (AUC) of blood glucose levels (incremental area above the baseline value) and perceived satiety (hunger, fullness, desire to

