eat, prospective food consumption and thirstiness) were calculated using the trapezoidal approximation (Winham et al., 2017). The maximum concentration (Cmax) of blood glucose levels were taken to be the highest concentration within the respective time interval (Stewart & Zimmer, 2017).

Nutritionist Pro was a dietary analysis software used for macronutrient and micronutrient analysis. This software consists of several food databases including the USDA Food Database, Canadian Food Database, Mexico Food Database and the Malaysian Food Composition Tables along with other hundreds of international food items. In this software, if the food item consumed by the participants was not available, the researchers can readily substitute it with other identical food items available in the databases. Besides, the standard recipe was created for food products that could not be found in any of the previously mentioned sources. The dietary intake of the participants for habitual, pre-test and test day were inserted in the software, and subsequently, the interested macronutrients (energy, carbohydrate, protein, fat, and dietary fibre) or micronutrients (calcium, magnesium, zinc, iron, selenium, Vitamin A, E, K, and C) were conveyed to SPSS for further analysis.

Bivariate and General Linear Model Analysis

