A paired t-test (normally distributed) or Wilcoxon matched pair signed-rank sum test (non-normally distributed) was used to compare the difference of two data between groups (placebo and intervention) on anthropometric measurements, blood glucose levels (iAUC and CMax), blood pressure, dietary intake, physical activity and perceived satiety (AUC). Two-way repeated measures ANCOVA was used to compare the postprandial blood glucose levels between two test products over different time points, controlling for treatment and time to test for treatment by time interaction after adjustment for covariates (age, ethnicity, gender and BMI) (Tongyu & Chong-Do, 2021; J. Wang et al., 2021). Rather than subtracting from baseline data alone, including baseline data as a covariate will improve the analyses' performance. Furthermore, due to random deviations at baseline, the use of baseline subtraction can result in artefactual effects (whether these differences are statistically significant or not) (Blundell et al., 2010). The perceived satiety was analysed using the Friedman non-parametric test. The analysis was considered significant at a p -value ≤ 0.05 . Any significant data was further tested using Wilcoxon matched pair signed-rank sum test.

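### The glucose time-course ANCOVA adjusts a within-person comparison for age, ethnicity, gender and BMI, which as additive terms do nothing and in an uncentred wide-format model can destroy the product test, and it names no fasting glucose value

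*SAP*

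**What the plan says.** The Protocol (Data collection) describes a two-product crossover: the test product is taken "together with the standardized breakfast in treatment sequences (AB, BA". At the test visit there is a "fasting capillary blood sample (baseline) withdrawal using the finger pricking method", and "postprandial blood samples as well as perceived satiety measurement were then taken at 30, 60, 90 and 120 min thereafter". The SAP (Data Checking and Normality Test) reports 30 complete records with nothing missing.

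Under the heading "Bivariate and General Linear Model Analysis" the SAP plans paired tests of iAUC and Cmax. It then plans a two-way repeated measures ANCOVA of postprandial glucose, to test "treatment by time interaction after adjustment for covariates (age, ethnicity, gender and BMI". Two general remarks follow: "Rather than subtracting from baseline data alone, including baseline data as a covariate will improve" the analysis, and "the use of baseline subtraction can result in artefactual effects". Neither names a variable, a visit or a model. The iAUC itself is defined under Descriptive Statistic as the "incremental area above the baseline value".

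The SAP names SPSS 21. It does not give the procedure, the data layout, the centring or coding of covariates, or the output to be read.

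**The concern.** In a crossover each person is their own control. A covariate that does not change between visits has nothing to explain in the difference between products. Three of the four listed covariates are fixed within a person and BMI is nearly so. The covariate that can differ between visits, fasting glucose, is missing from the list, although the SAP's next sentence argues for a baseline covariate.

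This is the only planned test of product by time on glucose. It is also the only planned glucose analysis that could carry baseline as a covariate, since iAUC subtracts baseline and Cmax ignores it. What the four covariates do depends on how the model is set up, and the SAP does not say. Two analysts following the text could report different answers from the same data.

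**Working it through.** The documents give no power, effect size, SD or covariate distribution, so there is no stated figure to reproduce. From the documents come n = 30, two products, four postprandial times, complete data and the 0.05 level. All else is assumed: age mean 25-45 (SD 5-15), BMI mean 25-30 (SD 3-6), gender 50/50, ethnicity 70/20/10, and a standardised paired difference of 0.53.

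**1. Additive terms (long-format mixed model).** Write glucose for person i, product k, time t as y_ikt = m_kt + g'x_i + u_i + e_ikt. In y_i1t - y_i2t the term g'x_i cancels, so with complete data x_i cannot move the product or product-by-time estimates. In four simulated data sets the product SE was identical with and without the four covariates (0.1375, 0.1303, 0.1225, 0.1091). One fasting value per person is just as inert: the mean of the two visits gave an SE ratio of 0.999.

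**2. Covariates crossed with product (wide GLM).** Each within-person contrast is regressed on the covariates, D_i = a + b'x_i + e_i, and the F table tests a, the effect at x = 0. Relative to no covariates, the SE of a is multiplied by sqrt(n [(X'X)^-1]_11).

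Hand check, age 35 (SD 10) and BMI 28 (SD 5), treated as independent: sqrt(1 + (35/10)^2 + (28/5)^2) = sqrt(1 + 12.25 + 31.36) = sqrt(44.61) = 6.7. Simulation, with gender and ethnicity effect-coded and estimation at n = 30, gives 7.44. Over seven settings the ratio is 6.2-12.2.

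Power, 4,000 simulations per setting (product-by-time contrast means assumed 0.5, 0.3, 0.2):

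| Handling | Product | Product by time |
|---|---|---|
| No covariates | 0.795-0.801 | 0.795-0.814 |
| Uncentred | 0.053-0.077 | 0.046-0.069 |
| Age and BMI centred; gender, ethnicity as factors | 0.463-0.478 | 0.424-0.449 |
| All columns centred | 0.788-0.800 | 0.789-0.808 |

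The third row falls short because effect-coded factors weight the ethnic groups equally. With groups of 21, 6 and 3, the equally weighted mean has variance (1/9)(1/21 + 1/6 + 1/3) = 0.0608, against 1/30 = 0.0333. The SE ratio is sqrt(0.0608 x 30) = 1.35, and with random group sizes 1.46-1.47. A separate run gave 51-53% product power for this row. Other category splits give 36-74% for product and 32-75% for product by time.

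**3. Type I error in the uncentred branch.** With no effect modification it is 4.0-5.9%. Now let the average product effect be zero, but let age shift the product difference by 0.3 SD per SD of age. At age 0 the difference is 0.3 x 3.5 = 1.05 SD in size. The SE is 7.44/sqrt(30) = 1.36, so the shift is 0.77 SE and a normal approximation rejects about 12% of the time. At 0.5 per SD the shift is 1.75/1.36 = 1.29 SE, or about 25%. Simulation gave 13-23%. Over more age and BMI settings the range was 10-55%, against 5-8% with centring and 4-6% for the paired t-test.

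**4. Fasting glucose.** Regressing the paired difference on the between-visit fasting difference changes the SE by about sqrt((1 - r^2) x 29/28). For r = 0, 0.2, 0.3, 0.5 this is 1.018, 0.997, 0.971, 0.881; simulation gave 1.017, 0.999, 0.973, 0.885. A baseline shift that is constant over time drops out of product by time: that estimate at 30 min was identical with and without baseline in all four data sets.

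This range does not carry over to a mixed model with one slope for the raw visit value, because that slope mixes between-person and within-person associations. With an assumed between-person slope of 1.5 and within-person slope of 0, the product SE rose from 0.102 to 0.124 (0.103 to 0.122 in a repeat run). Split into person mean and visit deviation it was 0.104. With a within-person slope of 0.5 the SEs were 0.110 without baseline, 0.114 with the raw value and 0.105 split.

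**The case against.** The strongest reply is that the large figures are conditional. They need a wide layout, uncentred covariates and a reader who takes the omnibus table. Estimated means at the covariate averages, with categories weighted to the sample, amount to centring, and then almost nothing is lost. With additive terms the four covariates do no harm. All of this stands. A reader might infer that the trial's time-course test had 5-8% power, but the documents do not support that, because the layout is not stated.

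A reader might also infer that the worst outcome is a missed effect and never a false one. That holds only if no listed covariate modifies the product effect, and the documents give no ground for assuming it.

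It can be said that the SAP already provides for baseline. It argues for a baseline covariate in general, so it would be wrong to say that it ignores baseline. But it does not say that fasting glucose enters this model, or whether as one value per person or one per visit, and that choice decides whether the term can do anything. It is also fair that baseline adjustment brings no gain for product by time, the test this ANCOVA is written for.

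Finally, BMI may be recalculated at each visit. The SAP does not say; the argument holds in full for age, ethnicity and gender.

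**Conclusion.** The concern holds in conditional form. Without condition: in this crossover the four listed covariates, as additive terms, cannot adjust the product or product-by-time contrasts (for BMI, to the extent that it is constant), and no fasting glucose value is named. Conditional on a wide GLM with uncentred covariates and the F table read: power falls from about 80% to 5-8% for product and 5-7% for product by time. Type I error is near 5% without effect modification and about 13-23% if age modifies the product difference by 0.3-0.5 SD per SD. These sizes rest on assumed covariate distributions and effect sizes; another set of assumed distributions gave SE ratios of 6.5-13.9.

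The baseline gain is modest and uncertain: an SE change of +2% to -11% for the product main effect in a paired-difference calculation, for assumed correlations of 0 to 0.5.

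A reader might infer that the whole glucose conclusion is compromised. It is not: the paired iAUC and Cmax tests do not use these covariates. Equally, calling the ANCOVA a supporting analysis is an inference, since the documents do not rank the glucose analyses.

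**What to change.** Drop age, ethnicity, gender and BMI from this analysis. Fit a linear mixed model to the 30, 60, 90 and 120 min values with product, time, product by time and period as fixed effects, participant as a random effect, and correlated times within visit. Enter fasting glucose as two terms, the person's mean over the two visits and that visit's deviation from it, rather than one raw value with a single slope.

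If the four covariates are kept, centre every covariate column, including the gender and ethnicity codes, or estimate the product difference with categories weighted to the sample. Centring age and BMI alone is not enough. State the layout and which tests are reported.

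The SAP already reports data checks on 30 participants, so label the change as post hoc and also report the ANCOVA as the SAP now words it. The cost is SAP wording and one re-run, with no new data. The statistical price of the baseline term is about one degree of freedom, and possibly a slightly larger SE if the between-visit correlation is near zero.

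### Friedman's test on the satiety ratings cannot test product-by-time, and the SAP leaves its ranked factor, Wilcoxon contrasts and multiplicity rule unstated (exploratory aim)

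*SAP*

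**What the plan says.** All the analysis statements are in the SAP, section Bivariate and General Linear Model Analysis.

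- Satiety ratings: "The perceived satiety was analysed using the Friedman non-parametric test".
- Threshold: "The analysis was considered significant at a p -value" of 0.05 or less, with no adjustment mentioned.
- Follow-up: "Any significant data was further tested using Wilcoxon matched pair signed-rank sum test". The pairs to be compared are not listed.
- Overall product comparison: the outcomes given a paired t-test or signed-rank test between placebo and intervention include "physical activity and perceived satiety (AUC").
- Postprandial glucose: a two-way repeated-measures ANCOVA, "controlling for treatment and time to test for treatment by time interaction". On baseline values, the section argues that "including baseline data as a covariate will improve" the analysis.

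The Protocol, section Data collection, sets the schedule. A pre-meal rating is part of the baseline assessments ("followed by a perceived satiety measurement and fasting capillary blood sample (baseline) withdrawal"), and "perceived satiety measurement were then taken at 30, 60, 90 and 120 min thereafter". Both products are taken with the same standardised breakfast in an AB/BA crossover. The SAP, section Descriptive Statistic, lists five satiety scales and computes a 2-hour AUC for them. The Protocol's opening section describes satiety as explored; the primary objective is glycaemic.

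**The concern.** There are two separate gaps.

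**The test does not fit the layout.** Each scale has two within-person factors, product and time. Friedman's test ranks the levels of one factor within each person. For glucose, taken at the same times in the same visits, the SAP specifies a product-by-time test. For satiety it specifies none.

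**The test is not fully specified.** With no ranked factor, contrasts or adjustment, two analysts could follow the SAP and run different tests. Under one reading, a response to the breakfast common to both products could open the way to unadjusted product comparisons at single times.

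At stake is any statement about when the products differ in satiety. AUC averages over 2 hours, so it has little power for a difference confined to part of that time and cannot show its timing.

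**Working it through.** The documents give no satiety SD, correlation or power, so there is no planned figure to reproduce.

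**1. Counts from the documents.** 2 products × 5 times = 10 cells per scale; 4 post-meal times × 5 scales = 20 matched-time product contrasts.

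**2. What each reading of Friedman on the ratings tests.**

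| Ranked factor | What it tests | Product-by-time? |
|---|---|---|
| 5 times within one product | change over time in that product | no |
| all 10 product-time cells | any difference among cells, including the shared meal response | not separable |
| 2 products at one time | product at that time; weaker than, and largely duplicating, its Wilcoxon follow-up | no |

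Friedman applied to within-person product differences across times could address the interaction, but the SAP does not describe that. Naming the ranked factor would therefore settle the ambiguity without supplying an interaction test.

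**3. Simulation assumptions.** Normal ratings, n = 30, AR(1) over time, effects in within-visit SDs. Results are shown for two assumed settings: between-scale correlation 0.3 with serial correlation 0.6 / 0.6 with 0.8. There were 3,000 runs per setting for steps 4 and 5, and 2,500 for step 6 unless stated.

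**4. Ten-cell Friedman, no product effect.** Ranges cover three meal-response shapes (sustained, partly recovering, fully recovering).

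| Shared meal effect | Significant |
|---|---|
| none (serial correlation alone) | 6.8% / 9.4% |
| 0.25 SD | 16.0–18.5% / 21.2–25.1% |
| 0.5 SD | 59.5–70.3% / 80.5–89.0% |
| 1 SD | 100% / 100% |

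**5. Follow-ups, if they are the 20 product contrasts.** For independent tests the chance of at least one false difference is 1 − 0.95^20 = 64.2%. With the assumed correlations:

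| Rule | At least one false product difference |
|---|---|
| ungated, unadjusted | 53.4% / 39.5% |
| after ten-cell gate, no meal effect | 21.6% / 23.1% |
| after ten-cell gate, meal effect 0.5 SD | 50.2–51.0% / 40.0–41.0% |
| after two-product Friedman gate | 34.2–36.6% / 25.8–28.3% |
| Holm over 20, ungated | 2.9% / 2.2% |
| per-scale joint test, then Holm over 4 | 10.9% / 7.1% across five scales |
| per-scale joint test, then Holm over 20 | 4.4% / 2.9% |

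At a 0.5 SD meal effect the ten-cell gate gives almost no protection.

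**6. What the AUC test covers.** Satiety AUC is taken as total area. Divided by 120 min, the trapezoidal rule weights the five times 1/8, 1/4, 1/4, 1/4, 1/8.

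- 0.5 SD at all four post-meal times: 0.5 × (1/4 + 1/4 + 1/4 + 1/8) = 0.4375 SD in mean AUC.
- 0.5 SD at 90 and 120 min only: 0.5 × (1/4 + 1/8) = 0.1875 SD.

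The joint test below is the 4-df test of product and product-by-time on the post-meal ratings, adjusted for baseline and period.

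| Product effect | Planned AUC | Baseline-adjusted AUC | Joint test |
|---|---|---|---|
| constant 0.5 SD | 58% / 47% | 75% / 81% | 53% / 67% |
| 0.5 SD at 90 and 120 min | 15% / 13% | 19% / 24% | 41% / 65% |
| ramp, 0 at 30 min to 0.5 SD at 120 min | 15% / 12% | 20% / 23% | 25% / 33% |

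A separate simulation of a gradual ramp (400 runs) gave 22% / 31% for the joint test and 32% / 40% for baseline-adjusted AUC. The order depends on how early the rise begins. A ramp of 0.125, 0.25, 0.375, 0.5 SD has mean AUC effect (0.125 + 0.25 + 0.375)/4 + 0.5/8 = 0.25 SD. One still at zero at 30 min (0, 1/6, 1/3, 1/2) has (0 + 1/6 + 1/3)/4 + 0.5/8 = 0.1875 SD.

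**The case against.** The best defence is that the section has a coherent, harmless reading: paired AUC compares the products, and Friedman with Wilcoxon describes change over time within each product. On that reading no product claim is at risk. The remaining error concerns which post-meal times differ from one another. With a sustained 1 SD meal effect, at least one of the six truly equal pairs is called different in 20% / 19%, per scale and product, but this is not a stated aim. The defence stands as far as it goes. The SAP does not say that this is the analysis, and it would still leave the time course without a product comparison.

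A reader might infer that satiety is never compared between products. The documents do not support this, because the AUC comparison does so. A reader might also take the 40–55% as the plan's error rate. It is not: the SAP lists no contrasts, so the figure describes one possible use of an open rule.

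It is also fair to say that Holm over 20 plain Wilcoxons would cure the false positives without a new model. Only the missing product-by-time test needs more. Part of the joint test's advantage over the planned AUC comes from baseline adjustment, and the late-step pattern favours it.

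**Conclusion.** The concern holds for product comparisons over time in an exploratory aim. As specified, no satiety analysis tests product-by-time. That follows from the form of the test and needs no assumption. The missing factor, contrasts and adjustment are a second gap; naming the factor would not close the first.

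The size depends on how the rule is read and on assumed SDs, correlations and meal effects. With all ten cells ranked, a shared 0.5 SD breakfast effect alone gives significance in about 60–90% of trials. Twenty unadjusted product follow-ups give at least one false difference in roughly 40–55%.

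A reader might extend this to the trial's main result. The documents do not support that: the primary objective is glycaemic and has its own analyses, and the satiety AUC comparison remains valid. The change should be made because it is cheap and the SAP already applies a suitable kind of method to glucose.

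**What to change.** 1. Keep the paired AUC comparison as the overall product test for satiety.
2. For the time course, replace Friedman, per scale, with the kind of two-factor repeated-measures analysis the SAP uses for glucose: product, time, product × time and period on the four post-meal ratings, with the pre-meal rating as covariate. Period is an addition to the glucose model. The SAP reports no missing values, so a multivariate test of within-person differences is feasible. If residuals are badly skewed, use a permutation version that reshuffles the AB/BA labels.
3. Compare products at single times with Holm over all 20 scale-by-time contrasts, and label them exploratory. Holm over four times within each scale does not control error across scales.
4. If Friedman is kept, use it only to describe change over time within a product, name the contrasts, and draw no product claim from it.

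**Cost.** SAP wording and re-analysis of existing ratings; no new data. There will be fewer nominally significant time points. The joint test gains power only for effects confined to part of the 2 hours. It loses to a baseline-adjusted AUC test when the effect is constant or rises gradually from the meal, which is a reason to retain an overall AUC test. Because the SAP reports completed data checks, the change must be declared post hoc and reported beside the original analysis.
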